Due to the high variability in UF outcome in the Tmed-004 study, the Carry Life® UF glucose dose setting was adjusted to enable a glucose dose up to 20 g/h. The system software (SW) was updated for use with a 50% glucose solution instead of the 20% glucose solution. The Tmed-007 study was performed with the updated device in order to determine the UF efficacy of three different glucose doses (11, 14, and 20 g/h) during a 5-hour treatment in comparison to a standard 4-hour 2.27% glucose CAPD dwell. The study included eight subjects of high (H) and high average (HA) peritoneal membrane transport characteristics and the results showed a significantly increased UF volume compared to the 2.27% CAPD dwell at all three doses. The UF volume with the Carry Life® UF treatment was  $646 \pm 256$ ,  $739 \pm 312$ , and  $863 \pm 380$  ml with the 11, 14, and 20 g/h glucose doses, respectively, compared with  $162 \pm 242$  ml for the control CAPD dwell. Glucose UF efficacy was significantly higher with Carry Life® UF treatments, being  $17.0 \pm 10.6$ ,  $14.5 \pm 7.7$  and  $12.4 \pm 6.8$  ml UF/g glucose absorbed with the 11, 14 and 20 g/h glucose doses, respectively, compared with standard  $5.9 \pm 7.8$  ml UF/g glucose absorbed with the control CAPD dwell. The sodium removal was proportional to the fluid removal, resulting in a sodium removal with the Carry Life® UF treatments which was 4-5 times higher than the CAPD dwell ( $86 \pm 27$ ,  $92 \pm 33$ ,  $110 \pm 37$  mmol/treatment with the 11, 14 and 20 g/h glucose doses, respectively, vs.  $21 \pm 33$  mmol/treatment with the control CAPD dwell). The dialysate glucose concentration was maintained between 1.6% to 2.2% glucose throughout the treatments in a dose dependent manner.

There were no incidents of adverse therapy or adverse device effects in Tmed-004. In Tmed-007 there was one adverse device effect where the subject felt light-headed after the 11 g/h Carry Life® UF treatment. The incident resolved after a short rest. All patients tolerated the treatment well and there was no discomfort associated with the intermittent transfer of IP fluid during the investigations.

Since the Tmed-007 study, the Carry Life® UF cycler has been updated in order to improve the robustness and usability of the system, including:

- The auto-drain function has been added.

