**Visit 3-4 (Carry Life® UF treatments)**

- A 5-hour Carry Life® UF treatments will be performed (Visit 3 using the 11 g/h glucose dose and Visit 4 using the 15 g/h glucose dose).
- A 1.36% glucose PD solution, 1.5–2 L according to the subject's standard prescription will be used for the initial fill and automatic drains will be performed hourly, which means that approximately 180 ml of dialysate will be removed by the system and transferred into a drain bag every hour. The dialysate will be analyzed according to Table 1.
- Venous blood samples for glucose measurement will be taken before treatment, at 30 min, at 1 hour and then hourly until the fifth hour (end of the treatment) via a peripheral intravenous cannula. If it is not possible to cannulate a subject, samples shall be taken by venipuncture before treatment, at 1 hour and 5 hours.
- Body weight, blood pressure and heart rate will be measured before and after the treatments. In addition, blood pressure will be measured in case of clinical symptoms suggestive of hypotension such as lightheadedness, dizziness, feeling faint, tiredness or weakness, change of consciousness e.g., drowsiness, nausea, and cold and clammy skin.

Subjects will be withdrawn from the rest of the study if they:

1. Experience a systolic blood pressure < 100 mmHg where the hypotension is deemed to be caused by hypovolemia due to excessive peritoneal UF.
2. Generate an UF rate higher than 20 ml/kg body weight/treatment.

If the 11 g/h glucose dose Carry Life® UF treatment results in a UF volume of 1.0 L or greater, the 15 g/h glucose Carry Life® UF treatment will not be performed.

Based on the UF volume obtained from the Carry Life® UF treatments the Carry Life® UF dose prescription for the home treatment phase will be determined according to the following criteria:

1. The 15 g/h glucose dose will only be used if both of the following conditions are met:
  - The treatment with the 11 g/h glucose dose achieved a UF volume of less than 1.0 L.
  - The treatment with the 15 g/h glucose dose achieved a UF volume 25% greater than the treatment with the 11 g/h glucose dose.
2. In all other cases the 11 g/h glucose dose will be used.

For example:

- The 11 g/h glucose dose gave a UF volume of 500 ml and 15 g/h glucose dose gave a UF volume of 700 ml UF (40% greater than the 11 g/h glucose dose) à the 15 g/h the Carry Life® UF glucose dose shall be used.

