- The 11 g/h glucose dose gave a UF of 500 ml and 15 g/h dose gave a UF of 620 ml (24% greater) à the 11 g/h Carry Life® UF glucose dose shall be used.
- The 11 g/h glucose dose gave a UF volume of 1000 ml à the 11 g/h Carry Life® UF glucose dose shall be used.

Before continuing to the randomization phase, the responsible physician will review the blood chemistry and blood glucose data generated during the in-clinic treatment phase, as well as and the occurrence of a systolic blood pressure of < 100 mmHg or, an UF rate exceeding 20 ml/kg body weight/treatment and confirm that the subject can proceed to the next phase of the study.

**Identification of efficacy evaluation days:** The patient, together with the physician, will confirm the scheduling of the four efficacy evaluation days which will take place during week 2 and week 4 of each study arm in the home treatment phase. For each patient, the efficacy evaluation days should be scheduled on the same day of the week, a Monday, Wednesday or Friday and the same time of the day.

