#### 6.2.3 Randomization phase

After completing the in-clinic treatment phase, subjects who will be prescribed the Carry Life® UF 11 g/h glucose dose will be randomized with an equal ratio into Group A (starting with the control arm) and Group C (starting with the Carry Life® UF arm). Subjects who will be prescribed the Carry Life® UF 15 g/h glucose dose will be randomized with an equal ratio into Group B (starting with the control arm) and Group D (starting with the Carry Life® UF arm) (refer to Figure 1). The randomization is being done to reduce any potential for bias based on subjects starting in the treatment or control arms.

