**Table 7. The tests methods, recording and analysis of variables**

Test/assessment	Required measurements	Recording	Analysis	Source data
PD fill volume	Weight of full PD bags with or without outer wraps. Weight of plastic material (may be predetermined).	In-clinic visits, PET, and Carry Life® UF treatments: Home phase efficacy evaluations treatments (control and Carry Life® UF).	Calculated by electronic data capture (EDC): The weight of full PD bags minus weight of the plastic material.	Work sheets for measured data and eCRF for calculated data.
Drained volume	Weight of drain bags. Weight of plastic material (may be predetermined)	All CAPD dwells and Carry Life® UF treatments during home phase.	Calculated by EDC: The sum of all volumes drained for each treatment, including all dialysate sample volumes.  The drained volume in each drain bag is calculated as the weight of the drain bag minus the weight of the plastic material.	Work sheets for measured data and eCRF for calculated data.
Treatment time (hours)	Time for end of peritoneal fill and start of peritoneal drain.		Calculated by EDC: Time between "end of peritoneal fill" and "start of peritoneal drain"	Work sheets for measured data and eCRF for calculated data.
Glucose volumeexact	Weight of full glucose bag with or without outer wrap. Weight of used glucose bag. Weight of plastic material (may be predetermined)	Carry Life® UF in-clinic treatments and Carry Life® UF efficacy evaluation treatments (ml).	Calculated by EDC; Weight of full glucose bag minus weight of used glucose bag (g) divided by the density of the 50% glucose solution (1.2235 g/ml).	Work sheets for measured data and eCRF for calculated data.
Glucose volumeapprox for Carry Life® UF home treatments other than efficacy evaluation days (ml)	None, nominal volume for the 5 hour Carry Life® UF treatment at each dose 110 ml (11 g/h) and 150 ml (15 g/h) is used.	Daily during Carry Life® UF arm	N/A	eCRF (prescribed Carry Life UF glucose dose).

Test/assessment	Required measurements	Recording	Analysis	Source data
UF volumeexact (ml)	PD fill volume. Glucose volume. Drained volume.	In-clinic visits, Home phase efficacy evaluations treatments	Calculated by EDC; Drained volume-PD fill volume - Glucose volume exact .	Work sheets for measured data and eCRF for calculated data.

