UF volumeapprox. (ml)	PD fill volume. Glucose volume. Drained volume.	All dwells/Carry Life® UF treatments during home phase.	Calculated by EDC; Drained volume-PD fill volume - Glucose volume approx.	Work sheets/electronic patient-reported outcome measures (ePROM) for measured data and eCRF for calculated data.
UF rate (ml/kg body weight/treatment)	UF volume exact . Body weight before treatment.	In-clinic phase, Carry Life® UF treatments.	Calculated by EDC; UF volume exact /Body weight before treatment.	Work sheets for measured data and eCRF for calculated data.
UF volume % increase	UF volume exact	End of In-clinic phase	Calculated by EDC; ([UF volume exact Visit4/ UF volume exact Visit3]-1)*100	eCRF
Dose determination	UF volume % increase	End of In-clinic phase	Determined by EDC according to dose determination algorithm.	
Dialysate glucose concentration	Glucose concentration in drain samples	In-clinic phase, PET, and Carry Life® UF treatments: PET: T0, T1h, T2h, T4h Carry Life UF: T0, T1h, T2h, T3h, T4h, T5h, peritoneal drain	Laboratory analysis	Laboratory data
Peak dialysate glucose concentration	Glucose concentration in drain samples	In-clinic phase, Carry Life® UF treatments: T1h, T2h, T3h, T4h, T5h	Data analysis	N/A
PET	Sodium and creatinine concentration in dialysate.	PET, at T0, T1 and T2 T4	D/P creatinine  Transfer type determined as D/P creatinine at 4h Low: 0.34-0.50 Low average: 0.50-0.65 High average: 0.65-0.81 High: 0.81-1.03  Sodium dip: Dialysate sodium: T1 minus T0	Laboratory data

Test/assessment	Required measurements	Recording	Analysis	Source data
Glucose absorption	PD fill volume. Glucose volume exact . Drain volumes (peritoneal drain + Carry life UF drain bag). Glucose concentration of drain volumes (peritoneal drain + Carry life UF drain bag).	In-clinic (Carry Life UF treatments) Home phase efficacy evaluations treatments (control and Carry Life® UF).	Sum of glucose added (PD fill volume (ml) * glucose concentration of PD solution (13.6 or 22.6 g/ml) + Glucose volume exact (ml) * 0.5 g/ml) minus the sum of glucose drained (peritoneal drain volumes * the glucose concentration of drain volumes (g/ml)).	Work sheets for measured data, laboratory data and eCRF for calculated data.

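### Table 7's percentage formula for the home glucose dose mis-signs the change when Visit 3 UF is negative, and can then point to 15 g/h although UF fell, contrary to section 6.2.2

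*Protocol*

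**What the plan says.** Three places in the protocol fix the home dose.

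- **Section 6.2.8, Table 7.** UF volume is defined as "Drained volume-PD fill volume - Glucose volume exact". The percentage increase is calculated from it by the EDC as "UF volume exact Visit4/ UF volume exact Visit3]-1)*100", where Visit 3 is the 11 g/h treatment and Visit 4 the 15 g/h treatment. The next row lists that percentage as its only required measurement and describes the dose as "Determined by EDC according to dose determination algorithm".
- **Section 6.2.2, Visit 3-4.** The higher dose is allowed only under two conditions. UF at 11 g/h must be below 1.0 L, and "The treatment with the 15 g/h glucose dose achieved a UF volume 25% greater than the treatment with the 11 g/h glucose dose". Then: "In all other cases the 11 g/h glucose dose will be used". All three worked examples use positive UF volumes.
- **Section 6.2.2, review before randomization.** The physician looks at blood chemistry, blood glucose, low systolic pressure and excessive UF rate in order to "confirm that the subject can proceed to the next phase of the study". The percentage and the assigned dose are not on that list.

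Attachment C (section 20.3), on setting the glucose dose, is listed by title only.

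**The concern.** UF volume is a signed difference with no floor at zero. Section 2.6 itself describes fluid re-absorption late in a CAPD dwell. Section 6.4.3 notes that measured UF also depends on fluid left behind before and after a dwell. A zero or negative value from a single in-clinic treatment is therefore possible, and the dose rests on one treatment per dose level.

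A ratio to baseline works as a percentage change only when the baseline is positive. With a negative baseline, a further fall gives a positive percentage and a rise gives a negative one. A negative Visit 3 value always satisfies the 1.0 L condition, so nothing else in the printed rule stops the wrong result. The in-clinic withdrawal criteria cover low blood pressure and high UF, not low UF.

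At stake is one subject's prescription. Someone whose net UF worsened at the higher glucose dose would be given that dose for the four-week device arm, with more glucose and no sign of a UF gain. This runs against the aim in section 3.5 of obtaining the required UF with as little glucose absorption as possible.

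**Working it through.** **Inputs.** The formula and the UF definition come from Table 7, and the dose rule from section 6.2.2. The pilot figures come from section 3.8 (Tmed-007, eight subjects): 646 ± 256 ml at 11 g/h and 739 ± 312 ml at 14 g/h. The latter stands in for 15 g/h. The planned enrolment is 25. The within-subject correlation between the two treatments is not given, so values of 0, 0.5 and 0.9 are assumed.

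**1. The protocol's own examples.** Write V3 and V4 for UF at Visits 3 and 4.

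- 500 to 700 ml: (700/500 − 1) × 100 = 40%, so 15 g/h.
- 500 to 620 ml: (620/500 − 1) × 100 = 24%, so 11 g/h.

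Both match section 6.2.2. For positive V3 the formula does what the rule says.

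**2. Negative V3.** The threshold is V4/V3 − 1 ≥ 0.25, that is, V4/V3 ≥ 1.25. Multiplying by a negative V3 turns the inequality round: V4 ≤ 1.25 × V3. The 25% mark is therefore reached exactly when V4 lies well *below* V3, and never when V4 is at or above V3.

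| V3 (ml) | V4 (ml) | Actual change (ml) | Table 7 result | Dose it points to | Section 6.2.2 |
|---|---|---|---|---|---|
| −200 | −300 | −100 | +50% | 15 g/h | 11 g/h (UF not greater) |
| −100 | −125 | −25 | +25% | 15 g/h | 11 g/h (UF not greater) |
| −100 | −124 | −24 | +24% | 11 g/h | 11 g/h |
| −100 | +300 | +400 | −400% | 11 g/h | 25% greater has no defined meaning; default 11 g/h |
| 0 | any | V4 | undefined | none | 25% greater has no defined meaning; default 11 g/h |

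The first two rows contradict section 6.2.2. The others do not.

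**3. How often the contradiction would arise.** The event is V3 < 0 and V4 ≤ 1.25 × V3. V3 and V4 are taken as bivariate normal with the pilot means and SDs.

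- P(V3 ≤ 0) = Φ(−646/256) = Φ(−2.52) = 0.0058 per subject. This is an upper limit for the event, not its probability.
- The joint probability p is found by numerical integration. The chance of at least one case in 25 is 1 − (1 − p)^25.

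| Assumed correlation | p per subject | At least one in 25 |
|---|---|---|
| 0 | 0.000026 | 0.07% |
| 0.5 | 0.00043 | 1.1% |
| 0.9 | 0.0022 | 5.3% |

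**The case against.** The strongest reply is that Table 7 is shorthand and section 6.2.2 governs. A fall from −200 to −300 ml is not a greater UF volume, so the governing text gives 11 g/h. The dose row already leaves out the 1.0 L limit, so it cannot show that the EDC has no further check. Attachment C and the EDC specification are not shown and may deal with the case. The event is rare, 15 g/h is a permitted dose already tried under supervision, and section 6.2.5 lets the physician adjust the prescription if fluid removal is inadequate.

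Most of this stands, and it limits the size of the point. It does not remove the mismatch: Table 7 prints an exact formula for the EDC, and on part of its range that formula disagrees with the rule it is meant to carry out.

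Three stronger readings are tempting, and the documents do not support them.

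- **A larger frequency.** On the Tmed-007 figures the chance of at least one Visit 3 UF at or below zero in 25 subjects is 1 − (1 − 0.0058)^25, about 14%. That counts any such value, and most of them do not lead to a contradiction. Tmed-004 (586 ± 685 ml) would give far more negative values. It had five patients, 8-hour treatments and a 20% glucose solution, and the device was changed afterwards.
- **Wrongly withheld escalation.** A subject whose UF rose from −100 to +300 ml stays at 11 g/h. This may be a poorer choice, but section 6.2.2 does not define 25% greater for a negative starting value and its default is 11 g/h, so it is not a conflict.
- **Damage to the trial's inference.** Randomization follows the prescribed dose ("subjects who will be prescribed the Carry Life® UF 11 g/h glucose dose will be randomized with an equal ratio into Group A", with the matching arrangement for 15 g/h), and section 7.1.6 pools the doses. The 1:1 allocation within dose and the primary test are not affected.

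**Conclusion.** The point holds as a narrow conflict between a printed formula and the rule it implements. When Visit 3 UF is negative and Visit 4 UF is at most 1.25 times that value, Table 7 points to 15 g/h although UF fell, while section 6.2.2 gives 11 g/h. When Visit 3 UF is zero, Table 7 gives no value.

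The algebra is certain; the frequency is not. The range of about 0.07% to 5% for at least one case in 25 subjects rests on a normal tail some 2.5 SDs from the mean of an eight-subject pilot, on 14 g/h standing in for 15 g/h, and on assumed correlations. The pilot enrolled only high and high-average transporters, a restriction this trial does not have. The values are rough, but all of them say rare.

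The consequence is confined to the home dose of the subject concerned. This is a low-priority correction, worth making because it is nearly free. It would already be settled in practice if Attachment C or the EDC algorithm holds a guard, although Table 7 should then be brought into line.

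**What to change.** In Table 7 and in the EDC dose algorithm, add two statements:

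1. The 15 g/h dose requires Visit 4 UF to exceed Visit 3 UF, in addition to the two existing conditions.
2. When Visit 3 UF is zero or negative no percentage is computed, and the existing default of 11 g/h in section 6.2.2 applies.

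Align Attachment C with this. The rule and the worked examples for positive Visit 3 UF stay as they are.

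The cost is a short addition to Table 7 and one EDC edit check, with no new data. The downside is that a subject with Visit 3 UF at or below zero whose UF rose at 15 g/h stays at 11 g/h. For negative Visit 3 values that is already the result under the printed formula. An objective rule of this kind is preferable to a case-by-case dose decision, because it keeps the assignment before randomization fully prespecified.

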### 2.1 SUMMARY DESCRIPTION OF THE INVESTIGATIONAL DEVICE AND ITS INTENDED PURPOSE

The intended use of the Carry Life® UF system is for peritoneal dialyses (PD) and ultrafiltration (UF). The therapeutic concept of the Carry Life® UF system is to maintain a stable intraperitoneal (IP) glucose concentration and thereby achieving a stable peritoneal UF. The Carry Life® UF system is indicated for PD and UF in adult patients with end-stage kidney disease (ESKD). Treatment with the Carry Life® UF system is prescribed by the treating physician and intended for use in dialysis clinics or in the home environment.

The Carry Life® UF system consists of the following parts:

[figure not shown]
- Carry Life® UF Cycler.
- Carry Life® UF Line set.
- Carry Life® UF Carrying bag.
- Carry Life® UF Storage bag.
- Battery and battery charger.

Treatment with the Carry Life® UF system also requires the following products:

- A standard PD catheter.
- A standard Baxter MiniCap extended life PD transfer set with twist clamp for access to the intraperitoneal catheter.
- A PD belt (Frank Stubbs).
- A 13.6 mg/ml glucose (1.36 %), 1.5 or 2L Baxter Peritoneal Dialysis solution.
- A 500 mg/ml, 500 ml Glucose Fresenius Kabi solution for infusion.

In this clinical investigation, subjects will already have a standard PD catheter and an extension set, and use the PD bags provided in their standard PD prescription. For participation in this clinical investigation, the Sponsor, or their designee, will provide the PD belt, and the glucose PD solution.

The Carry Life® UF Cycler with line set and glucose bag attached is illustrated in Figure 3.

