#### 7.1.7.3 Glucose ultrafiltration efficiency

Based on data gathered from the efficacy evaluation treatments during the home treatment phase of the study glucose ultrafiltration efficiency will be calculated. For each patient the average glucose UF efficiency (ml UF / g glucose absorbed) from the per protocol efficacy evaluation treatments in each arm will be used for the analysis. A paired comparison between the glucose UF efficiency achieved with the Carry Life® UF treatment ( $GlucEff_{CL}$ ) and the control CAPD dwell ( $GlucEff_{CAPD}$ ) per protocol treatments will be conducted. The average paired difference and the associated 95% CI will be calculated. Further, a t-test will be used to demonstrate that the Carry Life® UF treatment has a higher a glucose ultrafiltration efficiency than the control 2.27% CAPD dwell. The difference in glucose UF efficiency for each Carry Life® UF glucose dose and each fill volume compared to the control CAPD dwell will be summarized.

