#### 7.1.7.4 Peak dialysate concentration

During the in-clinic phase of the study the peak dialysate glucose concentration during the Carry Life® UF treatments will be determined from hourly dialysate sampling points, for each glucose dose. For this secondary endpoint, each subject is expected to have dialysate glucose data (T1h to T5h) from one in-clinic treatment at each Carry Life® UF glucose dose.

The average peak glucose dialysate concentration (in %; gram glucose per 100 ml fluid) for each glucose dose of the Carry Life® UF in-clinic treatments and the associated 95% CI will be calculated for the PP population. Further, a t-test will be used to demonstrate that the peak dialysate glucose concentration during the Carry Life® UF treatment is lower than 2.27%. The peak glucose concentration at each fill volume will be summarized.

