During the home treatment phase subjects will record clinical measurements and solution weights daily. Primarily, the subjects will enter the data (e.g., weight and blood pressure) into a mobile application. The data entered into the App will be transferred directly into the eCRF and there is no additional source documentation expected and thus these values are not subject to source data verification through the monitor. In case a subject does not use the App, but records data in a paper-based diary instead, the data are entered by dedicated site staff into eCRF and are subject for source data verification. However, in case of out of limit measurements the site is going to be alerted by means of a query and is going to follow-up with the patient to verify and discuss the entered data for any potential error. When copies of original source documents as well as printouts of original electronic source documents are retained, these shall be signed and dated by a member of the investigation site team with a statement that it is a true reproduction of the original source document. Copies of the source data shall remain at the clinical investigation site when the investigation is completed allowing an independent account of the investigation process.

The data from the eCRF will be managed in an EDC system. The EDC database will be programmed to use the input data from the eCRF to calculate output data including the endpoint measures (e.g., UF volume, peritoneal removal of the substances analyzed in the dialysate, and glucose efficiency). To be able to perform the calculation the following constants will be used:

- Glucose molecular weight: 180.16 g/mol.
- 50% glucose solution concentration: 0.5 g/ml.
- Density 50% glucose solution: 1.2235 g/ml.

Additionally plastic weights of solution bags and drain bags may be pre-weighed and used to calculate fill and drain volumes.

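### Table 7 computes absorbed glucose with PD-solution strengths in the wrong unit (a factor of 1000), and 22.6 does not match the 2.27% solution in any unit

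*Protocol*

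**What the plan says.** The glucose absorption row of Table 7 (Protocol section 6.2.8) gives the calculation. It starts with "Sum of glucose added (PD fill volume (ml) * glucose concentration of PD solution", and the strengths in that entry read "glucose concentration of PD solution (13.6 or 22.6 g/ml". The device's 50% glucose is then added and the drained amount removed: "ml) * 0.5 g/ml) minus the sum of glucose drained". Drain concentrations are also stated in g/ml.

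Elsewhere the protocol gives the strengths differently:

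- Section 2.1 lists "A 13.6 mg/ml glucose (1.36 %), 1.5 or 2L Baxter Peritoneal Dialysis solution".
- Table 4 (section 3.3) puts 27.2 g of glucose in 2 L of the 1.36% solution and 45.4 g in 2 L of the 2.27% solution.
- Section 7.1.7.4 expresses concentration "in %; gram glucose per 100 ml fluid".

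Section 7.1.7.3 takes, for each patient, the "average glucose UF efficiency (ml UF / g glucose absorbed) from the per protocol efficacy evaluation treatments in each arm" and compares the arms by a paired t-test; section 5.2 states the hypothesis. Section 8.1 says the database will be programmed to compute endpoint measures, glucose efficiency among them, and introduces its list with "To be able to perform the calculation the following constants will be used". The list holds the molecular weight of glucose and the concentration and density of the 50% solution. It gives no PD-solution strength.

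**The concern.** The other two terms of the formula come out in grams, so a fill term 1000 times too large swamps them. A constant scale error across the whole denominator would cancel in the device-to-control ratio. This one does not, because it inflates only one of the terms.

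The digit is a separate matter. If someone corrects the unit and leaves 22.6, the result looks plausible and affects only the control arm.

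At stake are a tested secondary endpoint and the performance claim on glucose UF efficiency in section 5.3. The formula in Table 7 is the only place in the protocol where a calculation states these two strengths.

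**Working it through.** **1. Correct strengths from the protocol.** With % as g per 100 ml, 1.36% = 0.0136 g/ml and 2.27% = 0.0227 g/ml. Table 4 agrees: 27.2/2000 = 0.0136 and 45.4/2000 = 0.0227. Section 2.1 agrees for the weaker solution (13.6 mg/ml).

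**2. Can 22.6 be recovered?** As g/L or mg/ml it is 2.26%; as g per 100 ml it would be 22.6%. The hydrate form does not explain it: the footnote to Table 9 equates 2.5% monohydrate with 2.27% anhydrous. Taking water as 18.015 g/mol (an assumption, not in the protocol), 25 × 180.16/198.175 = 22.73 g/L. The printed entries exceed the correct ones by 13.6/0.0136 = 1000 and 22.6/0.0227 = 995.6; the second ratio differs because the digit is wrong too.

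**3. Fill term as printed and as it should be.**

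| Fill | Solution | As printed | Correct |
|---|---|---|---|
| 2 L | 1.36% | 2000 × 13.6 = 27,200 g | 27.2 g |
| 2 L | 2.27% | 2000 × 22.6 = 45,200 g | 45.4 g |
| 1.5 L | 1.36% | 1500 × 13.6 = 20,400 g | 20.4 g |
| 1.5 L | 2.27% | 1500 × 22.6 = 33,900 g | 34.05 g |

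**4. Effect of the literal formula (illustration).** Inputs are the Tmed-007 means in section 3.8: device at 11 g/h, UF 646 ml and efficiency 17.0 ml/g; control, UF 162 ml and 5.9 ml/g. The pilot control was a "standard 4-hour 2.27% glucose CAPD dwell", not the 5-hour dwell of this trial. A 2 L fill is assumed, and absorption is back-calculated from ratios of means, so the figures are approximate.

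- Absorbed: 646/17.0 = 38.0 g (device); 162/5.9 = 27.46 g (control).
- Device glucose added: 110 ml × 0.5 g/ml = 55 g.
- Drained: 27.2 + 55 − 38.0 = 44.2 g (device); 45.4 − 27.46 = 17.94 g (control).
- Denominator as printed: 27,200 + 55 − 44.2 = 27,210.8 g (device); 45,200 − 17.94 = 45,182.1 g (control).
- Efficiency as printed: 646/27,210.8 = 0.024 ml/g; 162/45,182.1 = 0.0036 ml/g.
- Drained glucose as a share of the denominator: 44.2/27,210.8 = 0.16%; 17.94/45,182.1 = 0.04%.

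The device-to-control ratio moves from 17.0/5.9 = 2.9 to about 6.6, so the error does not cancel between arms.

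**5. Effect if only the unit is corrected and 22.6 stays.** Control absorption is understated by 0.0001 g/ml times the fill volume: 0.20 g for 2 L, 0.15 g for 1.5 L.

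- 2 L: 162/(27.46 − 0.20) = 5.94 ml/g, up 0.7%. The difference falls from 11.10 to 11.06 ml/g (−0.4%).
- 1.5 L: 162/(27.46 − 0.15) = 5.93 ml/g, up 0.5%. The difference falls to 11.07 ml/g (−0.3%).
- Using Table 4's 32 g absorbed from 2 L over 4 hours instead: 32/31.8, up 0.6%.

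**The case against.** The strongest reply is that this is a typing error with little consequence. A 2 L bag holding 27 or 45 kg of glucose is impossible, and the correct values can be read from sections 2.1, 3.3 and 7.1.7.4, so the unit slip would very likely be caught before any result was reported. The digit error moves the difference by 0.03 to 0.04 ml/g, while the pilot standard deviations for this endpoint were 7.8 ml/g (control) and 10.6 ml/g (11 g/h). No wrong conclusion has been shown. These points stand, and they limit the importance of the finding.

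Three further qualifications are fair:

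- The digit error works against the device only where control UF is positive. With a negative value, a smaller denominator makes control efficiency more negative, which favours the device. Pilot control UF was 162 ± 242 ml, so some negative values are plausible.
- Section 8.1 also says dialysate data will not be entered in the eCRF, so it is unclear whether the database or a later analysis would run this formula.
- Fill and drain volumes are taken from bag weights with no density correction, so the formula is already approximate. The absence of the strengths from the section 8.1 list is not itself an error, since such constants may sit in other study documents.

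None of this makes the printed entry right. Whoever programs the calculation will take it from Table 7, and a specification should not rely on the programmer noticing that it conflicts with three other sections.

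**Conclusion.** The entry is wrong in two ways, and both follow from the protocol's own figures. The unit overstates the fill term by a factor of 1000; applied literally, the endpoint would no longer measure absorption. The effect of that on the t-test is not established, because the variance changes along with the means. The digit 22.6 matches the 2.27% solution in no unit. If it survived a unit correction, control efficiency would rise by about 0.5 to 0.7%, a negligible shift beside the pilot variability. The efficiency figures rest on pilot group means, a 4-hour control dwell and assumed fill volumes; the size of the fill-term error needs none of these. The primary endpoint and sample size are untouched. The error should be corrected before the calculation is programmed.

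**What to change.** In the glucose absorption row of Table 7, replace the two strengths by 0.0136 and 0.0227 g/ml; these reproduce Table 4 exactly. As a convenience, add both to the constants in section 8.1 so that the calculation draws them from one place. The cost is one corrected table cell and two added lines. Data collection, design and treatment are unchanged.
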